3.10.2.6 Treatment of Missing Data

For the primary endpoint requiring a valid weekly average home BP value preceding the Randomization and Week 4 visits, if a participant does not have a valid endpoint measure, that value will be flagged as missing and requiring imputation. In all cases it is the final BP weekly average that will be imputed for each time interval, not each component measure used to calculate the average. Imputations will be performed separately by analysis set, as required (i.e., Randomized Set, Per Protocol).

For missing Baseline (prior to Randomization) SBP results, missing data are considered missing at random and a multiple imputation will be applied.

For post-Randomization missing data, a Retrieved Data Multiple Imputation will be applied to account for the occurrence of intercurrent events which aligns to the Treatment Policy Strategy for handling of Intercurrent Events:

- 1) Participants with missing Baseline measurements will be assumed to have data missing at random and will have results imputed from the full baseline sample of participants (pre-randomization).
- 2) Participants with missing Week 4 home BP assessments and experiencing intercurrent events will have their result imputed for the primary analysis using multiple imputation. Participants with intercurrent events will have their missing result based on other participants with intercurrent events within the same treatment group.
 - a. Receive Wrong Treatment: Participants who received the wrong treatment and have missing

Week 4 results will have results imputed from the sample of participants who received the same treatment.

- b. Participants who discontinue treatment for reasons related to study treatment or study procedures will be imputed using a control-based imputation from the sample of participants with intercurrent events and randomly assigned to placebo.
- 3) Participants non-adherent to study treatment: Participants who were non-adherent to study treatment during Period 2 with missing Week 4 home BP measurement will be imputed from the sample of participants with intercurrent events and randomly assigned to placebo.
- 4) Participants with missing Week 4 home BP assessments who were adherent to study treatment and did not experience intercurrent events will have their results imputed for the primary analysis using multiple imputation. Participants without intercurrent events will have their missing result based on other participants also without intercurrent events and within the same treatment group.

If there is not a sufficient sample size to perform multiple imputations as described, participants with and without intercurrent events will be included in the source sample for imputation.

Multiple imputation (MI) will be applied, replacing each missing average SBP home assessment with a set of plausible values from the identified subsample, listed above. This will represent the uncertainty of the correct value based on the observed results. The multiply imputed datasets will be analyzed using standard procedures for complete data with their results combined with a variance-adjustment. The multiple imputation will be computed as follows:

- 1) Imputation:
 - a. For missing baseline, a regression method will impute missing data from the overall randomized sample.
 - b. For missing Week 4 SBP results, a regression method will impute missing data from the respective subsample with or without intercurrent events, as specified above and within the respective treatment group. Imputation will be performed using a Fully Conditional Specification (FCS) model using the regression method and will include the following factors:
 - Age, sex, race, BMI and ethnicity
 - Patient smoking and alcohol consumption
 - Baseline (at Randomization) average home SBP
- 2) Analysis: The final multiple imputed datasets will be analyzed using Rubin's Rule.

Proc MI and Proc MIANALYZE in SAS will be used to generate the datasets and run the analyses.

Sample SAS Code:

```
PROC MI DATA = SBP OUT = SBP2 SEED = 20231010 NIMPUTE = 100
  MINIMUM = . . . . . . . . 80  ROUND = . . . . . . . . . . 1
  MAXIMUM = . . . . . . . . 200  MINMAXITER = 5000 SIMPLE NOPRINT;
  FCS REG(BASE = TRTPN AGE SEX RACE BMI ETHNIC SMK ALC/ DETAILS);
  FCS REG(SBP4 = TRTPN AGE SEX RACE BMI ETHNIC SMK ALC BASE / DETAILS);
  CLASS TRTPN SEX RACE ETHNIC SMK ALC;
  VAR TRTPN AGE SEX RACE BMI ETHNIC SMK ALC BASE SBP4;
  RUN;
*SBP2 will be reformatted into an analysis dataset, here titled ADEFF with
each observation on a separate line;
>Note that in actual implementation, the imputations will be done
separately for those with intercurrent events and those without
intercurrent events. Note also that baseline values will be imputed from
all observations.;

PROC MIXED DATA = ADEFF EMPIRICAL METHOD = REML;
  BY IMPUTNUM;
  CLASS SITEID TRTP;
  MODEL AVAL = BASE TRTP / CL;
  REPEATED / SUBJECT = SITEID TYPE = CS;
  WHERE VISIT IN ('WEEK4');
  LSMEANS TRTP / DIFF CL ALPHA=0.05;
  ODS OUTPUT COVPARMS = CP LSMEANS = LSM DIFF = DIFFS;
  RUN;
PROC SORT DATA = DIFF;
  BY TRTP _TRTP;
  RUN;
PROC MIANALYZE DATA = DIFF ALPHA = 0.05;
  BY TRTP _TRTP;
  WHERE TRTP NE 3 AND _TRTP = 3;
  *TRTP = 3 corresponds to placebo in this example;
  MODELEFFECTS ESTIMATE;
  STDERR STDERR;
  ODS OUTPUT PARAMETERESTIMATES=SBP_PROP;
  RUN;
```

TRTPN is the planned treatment group, SEX is the sex of the participant, RACE is participant race, ETHNIC is participant ethnicity, SMK is participant smoking status, ALC is alcohol use. BASE is the baseline (at Randomization) average SBP value and SBP4 is the average SBP value at FU1/Week 4. The minimum and maximum values for SBP imputation may be modified according to the observed minimum and maximum within the sample. If the multiple imputation models cannot converge, model reduction (excluding covariates) may be performed.

For binary endpoints with missing results, a single value imputation of “failure” will be performed for analysis ([Section 3.10.1.2](#)).

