2.5 Sample Size

A total of 250 participants will be randomized: 100 for each of the GMRx2 doses and 50 for placebo group. As noted in Section 12.3 of the protocol, for the comparison of triple $\frac{1}{2}$ vs placebo at week 4, a sample size of 150 participants at a ratio of 2:1 will provide 99.7% power to detect a difference of at least 9 mmHg in mean home SBP, assuming a standard deviation of 11 mmHg. Similarly for the comparison of triple $\frac{1}{2}$ vs placebo at week 4, a sample size of 150 participants at a ratio of 2:1 will provide 100.0% power to detect a difference of at least 13 mmHg in mean home SBP, assuming a standard deviation of 11 mmHg. Therefore, the power for the two comparisons versus placebo will be 99.7% (since $0.997 \times 1.0 = 0.997$). Note that this is a simple, conservative sample size calculation by intention – the actual experimental design and subsequent statistical modelling approach will provide greater power than this.

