3.3 Multiplicity Adjustment

All tests are to be two-sided with a nominal level of α set at 5%. Since the purpose of the trial is to demonstrate effects on both of the GMRx2 dose versions versus placebo comparisons simultaneously for the designated primary endpoint (i.e., each GMRx2 dose has to be statistically significantly superior at two-sided $p<0.05$ to placebo for the trial to be regarded as positive), there is no need for adjustment of the Type I error for the primary endpoint, according to ICH E9 Guidance and FDA Guidance 'Multiple Endpoints in Clinical Trials. Guidance for Industry, 2022'.

The secondary efficacy parameters measure different aspects of the same underlying treatment effect evaluated in the primary efficacy endpoint, that is the effect of GMRx2 compared to placebo on blood pressure and do not demonstrate additional new treatment effects of the drug, but rather clarify the effect already demonstrated by the primary analysis. No type I error adjustment is proposed to adjust secondary efficacy endpoint analyses.

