3.9 Adherence

3.9.1 Adherence to Trial Medication

The planned daily dose is 1 pill per day. Adherence to trial medication will be computed overall and separately for each randomized group.

Trial medication adherence will be computed separately for the 2-week run-in period and the post-randomization treatment period (from randomization to FU1/Week 4) and will be assessed using the following parameters:

- Denominator: Planned number of pills for the period is defined as the number of days between the scheduled first and last treatment intake. The medication log CRF will be used to determine the number of expected days by computing the number of days between the start and stop dates for each record and summing across all records reported for each participant. Note, if there is a gap between the stop and start records for sequential medication logs, gap days will be assigned an expected count of 0.
- Numerator: The number of pills taken is measured via pill counts and numbers of pills returned. For participants with missing pill-return data, it will be assumed that the number of pills taken equals the minimum of the number of pills dispensed for that period and the number of days between the logged start and stop dates for the corresponding trial medication log.

Adherence to trial medication will be calculated as numerator/denominator and expressed in percentage. Adherence is confirmed if $\geq 80\%$ and $\leq 120\%$.

Additional details surrounding the calculations of numbers of pills dispensed and adherence will be described in a separate specifications document.

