3.9.3 Protocol Deviations

Over a blind review meeting, before database lock and unblinding, the different protocol deviations will be classified as minor or major and categorized by type (e.g. non-compliance to treatment, prohibited medication etc.) by the clinical teams. The number of major protocol deviations will be summarized by type of deviations. All protocol deviations will be listed.

Major protocol deviation categories include, but are not limited to:

- Randomized even though ineligible (not including minor non-safety related reasons such as miscalculation of run-in adherence)
- Received the wrong treatment
- Non-adherence to study treatment (adherence $< 80\%$ or $> 120\%$), for reasons known to be unrelated to tolerability or efficacy eg. participant moved overseas
- Interruption to study treatment as a result of supply chain issues in which protocol-specified procedures were not followed,
- Insufficient valid home BP measurements for home blood pressure calculation at randomization or follow-up visit 1.

A summary table will present the tabulations by major protocol deviation on the Screened Set. All protocol deviations will be listed.

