3.10 Analysis of the Efficacy Endpoints

3.10.1 Estimand

3.10.1.1 Primary Estimand

The population for the primary estimand includes adults (aged ≥ 18 years) with hypertension. The variable of interest is the difference between home measured SBP after Week 4 of treatment post-randomization and the home measured SBP in the week prior to randomization. The primary analysis will be performed on the Randomized Set including all participants who were randomized to treatment.

Intercurrent events for the primary analysis are listed below:

- Received the wrong treatment (i.e. a treatment other than the randomly assigned treatment)
- Discontinuation from the study treatment for reasons related to the study protocol or study treatment, such as lack of efficacy, tolerability, or adverse event.

For the primary analysis, the Treatment Policy Strategy will be applied where intercurrent events that do not result in missing BP measurements are considered irrelevant and data will be analyzed regardless of the occurrence of the event. The use of a Treatment Policy Strategy most closely aligns to an ITT analysis, where all available and imputed data contribute toward the estimated treatment effects. Participants with intercurrent events and missing data will have imputations performed from those participants with intercurrent events and non-missing data (Section 3.10.2.6). Participants without intercurrent events and missing data will have imputations performed from those participants without intercurrent events and non-missing data.

The primary analysis will be performed using a mixed model for repeated measures (MMRM). Sensitivity analyses adjusted for covariates are planned for the primary endpoint (Section 3.10.2.3). Subgroup analyses will also be performed among the primary analysis set (Section 3.10.2.5).

Supplemental analyses will be performed among the following analysis sets:

- 1) Full Analysis Set, including participants who have taken at least 1 dose of study treatment post-randomization and applying imputation methods in the same manner as the primary analysis methods (analysis to be performed if samples differ by $>5\%$)

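### SAP 3.10.2.6 would impute GMRx2 participants with pill counts above 120% from placebo donors, and does not bar placebo-assigned participants given GMRx2 from that donor pool

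*SAP*

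**What the plan says.** The primary analysis uses multiple imputation, and SAP 3.10.2.6 decides whose data supply each missing Week 4 value.

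- **Item 2b** covers participants who stop treatment for reasons related to treatment or study procedures. It calls the method control-based and draws "from the sample of participants with intercurrent events and randomly assigned to placebo".
- **Item 3** reads: "Participants who were non-adherent to study treatment during Period 2 with missing Week 4 home BP measurement will be imputed from the sample", and names the same placebo pool. It gives no adherence threshold and no direction.
- **Item 4** imputes from the participant's own arm, but only for those who were adherent and had no intercurrent event.
- **Fallback**: if the sample is too small, participants with and without intercurrent events both become donors. No numeric trigger is given.

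The terms are defined elsewhere. SAP 3.9.1 says: "Adherence is confirmed if $\geq 80\%$ and $\leq 120" per cent. SAP 3.9.3 lists as a major deviation: "Non-adherence to study treatment (adherence $< 80\%$ or $> 120" per cent), there limited to reasons known to be unrelated to tolerability or efficacy. SAP 3.10.1.1 names two intercurrent events. One is related discontinuation; the other is: "Received the wrong treatment (i.e. a treatment other than the randomly assigned treatment"). Non-adherence is not on that list. The same section says that participants without intercurrent events are imputed from others without them.

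**The concern.** Control-based imputation is meant to give people who lost the drug effect a value typical of people off the drug. Two features of the text work against that.

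1. A pill count above 120% is no evidence that the drug effect was lost. Pills taken are derived from pills returned, so pills that are mislaid can also raise the count. Item 4 nevertheless shuts such a participant out, and item 3 sends a GMRx2 participant to placebo donors. This pulls the estimate toward no effect.
2. The donor pool is defined by assigned treatment plus any intercurrent event. The only other randomized treatments are the two GMRx2 doses, so a placebo-assigned participant who received the wrong randomized treatment received GMRx2. With an observed Week 4 value, that person is a donor, and an on-drug pressure stands in for an off-drug one. This moves imputed GMRx2 values in favour of GMRx2.

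At stake is whether the main analysis of the primary endpoint can be programmed as written without either misplacing such a participant or departing from the text without a stated rule.

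**Working it through.** **Inputs.** Effects of 9 and 13 mmHg and SD 11 mmHg (Protocol 12.3, SAP 2.5); 100 and 50 per comparison as planned; 295 randomized (SAP 2.6.1), taken as 118:118:59 on the 2:2:1 ratio (the actual split is not given). On testing: "All tests are to be two-sided with a nominal level of α set at 5" per cent (SAP 3.3).

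**The plan's own figures.** SAP 2.5 says that "a sample size of 150 participants at a ratio of 2:1 will provide 99.7% power to detect a difference of at least 9 mmHg". Planned standard error = 11 × √(1/100 + 1/50) = 1.905. 9/1.905 = 4.72; 4.72 − 1.96 = 2.76; power = 99.7%, as stated. For the other comparison the SAP says the sample "will provide 100.0% power to detect a difference of at least 13 mmHg in mean home SBP"; 13/1.905 = 6.82 gives 100.0%. Both reproduce. (SAP 2.5 labels both comparisons triple ½, whereas Protocol 12.3 gives 9 mmHg to triple ¼. This does not affect the arithmetic.)

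**Tracing a GMRx2 participant above 120%, no intercurrent event, Week 4 missing.**
- Item 2: not applicable, since there is no intercurrent event.
- Item 4: not applicable, since adherence is not confirmed above 120%.
- Item 3: applies, so donors are placebo-assigned with intercurrent events.
- SAP 3.10.1.1: donors should be participants without intercurrent events. The two sections conflict.

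**Tracing a placebo-assigned participant given GMRx2, Week 4 observed.**
- Has an intercurrent event (wrong treatment) and was assigned placebo, so meets the donor definition in 2b and 3.
- Item 2a goes by treatment received, but only in choosing donors for a wrongly treated participant whose own value is missing. It removes nobody from the 2b/3 pool.

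**Size, first rule.** Each misplaced participant is imputed about 9 to 13 mmHg too high. Arm-mean shift = δ/118: 9/118 = 0.08 and 13/118 = 0.11 mmHg, against GMRx2. Even if 10% of the dose 1 arm were affected, the shift would be 0.10 × 9 = 0.90 mmHg, and planned power at 8.1 mmHg is still 98.9%.

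**Size, second rule.** One treated donor among k lowers the pool mean by δ/k. With a share m of a dose arm imputed from the pool, the arm mean shifts by m × δ/k. Taking m = 5% (assumed):

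| Donor pool | Pool-mean shift, mmHg | Arm-mean shift, mmHg |
|---|---|---|
| k = 3 | 3.0 to 4.3 | 0.15 to 0.22 |
| k = 6 | 1.5 to 2.2 | 0.08 to 0.11 |
| Fallback to all 59 placebo | 0.15 to 0.22 | about 0.01 |

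The small values of k are plausible for the unwidened pool. At assumed placebo intercurrent-event rates of 2–10%, with 50–100% of Week 4 values observed, 59 placebo participants give 59 × 0.02 × 0.5 = 0.6 to 59 × 0.10 × 1 = 5.9 donors.

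**Yardstick.** Standard error at 118 vs 59 = 11 × √(1/118 + 1/59) = 1.75 mmHg. The largest treated-donor shift in the table, 0.22, is 0.22/1.75, about one eighth of it.

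**The case against.** The strongest reply is that the people concerned may not exist.

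- The first rule needs a count above 120% and no valid home reading at all in the seven days before Week 4: one reading is enough for an average (SAP Table 3-2), and readings transmit automatically (Protocol Appendix 3). Where pill-return data are missing, SAP 3.9.1 caps pills taken at the logged days, so the count cannot exceed 100%.
- The second needs a dispensing error, although the database selects the kits (Protocol 10.3.5).

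All of this stands. A reader might infer that such participants are in the data, but the documents report none.

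Item 3 does not define non-adherence, the 3.9.3 wording is a qualified deviation category, and 3.9.1 leaves further detail to a separate specifications document. So 3.9.3 alone would not carry the reading. The 80–120% range in 3.9.1 does, as the only definition of adherence the SAP gives. One could also defend treating a count above 120% as unreliable exposure, but the SAP gives no such reason and 3.10.1.1 points the other way.

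The imputation regression has eight predictors, which three to six donors cannot support. Covariates would be dropped or the fallback used, and the fallback dilutes the second shift. This is why its range starts near 0.01 mmHg. The fallback does not remove the treated donor.

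A reader might also infer that the second rule inflates the reported effect. Under the treatment policy strategy, that participant's own pressure stays in the placebo mean and lowers it by 9/59 to 13/59 = 0.15 to 0.22 mmHg, against GMRx2. With k = 3 and 5% imputed the net is about zero, and with k = 6 it is against GMRx2. Net inflation is therefore not shown, though an on-drug value is still the wrong basis for a control-based imputation.

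**Conclusion.** The point holds as a specification flaw in the main analysis of the primary endpoint. On the SAP's own definitions, item 3 would impute an over-count GMRx2 participant from placebo donors, in conflict with 3.10.1.1, and the 2b/3 pool would admit a GMRx2-treated donor. Whenever either case occurs, the imputed value comes from the wrong people.

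The size is small, and the imputation biases run in opposite directions: about 0.1 mmHg per over-count participant against GMRx2, and about 0.01 to 0.2 mmHg for one treated donor in its favour. These figures rest on the planned effects, a 118:118:59 split, 5% of a dose arm imputed from the pool, and the pool sizes shown; the documents give no counts. They do not support a claim that significance is at risk or that the trial's conclusion would be wrong. The case for acting is that the correction is specific and nearly free.

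**What to change.** Four wording changes in SAP 3.10.2.6, to be made before unblinding so that donor choice cannot depend on results:

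1. **Item 3**: limit it to participants with adherence below 80%.
2. **Item 4**: extend it to participants with adherence of 80% or more, including above 120%, and no intercurrent event. Without this change, those above 120% would match no rule. It also agrees with 3.10.1.1.
3. **Donors for items 2b and 3**: define them as placebo-assigned participants with an intercurrent event who did not receive GMRx2.
4. **Fallback**: apply the same exclusion of GMRx2 recipients when that pool is widened; otherwise the excluded donor can return.

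Item 3 would still depart from 3.10.1.1 for participants below 80% without an intercurrent event, so 3.10.1.1 should name that exception.

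No new data are needed. The cost is that the donor pool may lose a participant, which makes the fallback slightly more likely.

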Selection of a single session per half-day period	
• Each day is divided into two half-days – AM and PM.• If more than one session occurs in one period e.g., two sessions in the AM period of a given day, one session only will be selected for use using two prioritisation steps:
– Sessions containing three or more BP measures will be prioritised over those with two. Those with only one BP measure will be used as a last resort.– If the first step does not uniquely select one session for the period, the earliest session of those selected in the first step will be used.
Calculation of averages	
• To calculate an average, perform a simple, unweighted mean of the flagged BP measurements in the selected sessions for the period of

	
interest.
 
– At Randomization: A minimum of 6 measures (e.g. ≥ 2 sets of triplicate measures or ≥ 3 sets of duplicate measures) are expected, including at least 1 morning and 1 evening, each with ≥ 2 measures per protocol-specified eligibility criteria.– Post-Randomization: At least 4 consecutive calendar days (8 measurement sessions, 24 BP readings) were recommended.– Calculations: For all timepoints, calculations of averages will be performed if there is at least 1 valid BP measurement.• The home BP values for the purpose of Baseline, FU visit 1 Week 4 are averages (as defined above) up to 7 calendar days immediately preceding each in-clinic visit.
– Each of the up to 2 selected sessions per day (1 morning and 1 evening) may be included in the calculation.• Days with no valid measures reported will be excluded from the calculation (i.e., only days with SBP measurements recorded will be included in average).
--	---

In addition, for descriptive plots of SBP and DBP measurements post-randomization, weekly average BP will be computed where Week is defined in relation to the randomization date with Week 1 initiating on Day 1, the first treatment with randomized trial medication:

Week = (date of BP measurement – date of first dose of randomized treatment)/7
Week is rounded up to the nearest integer. Averages will otherwise be calculated in the same manner as described in [Table 3-2](#).

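### The imputation model for missing Week 4 home SBP ignores the weekly on-treatment home SBP already collected; adding it for adherent, event-free participants is a cheap, minor improvement

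*SAP*

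**What the plan says.** SAP 3.10.2.6 gives a fixed list of predictors for missing Week 4 home SBP: "Imputation will be performed using a Fully Conditional Specification (FCS) model using the regression method and will include the following factors", followed by age, sex, race, BMI, ethnicity, smoking, alcohol and baseline home SBP. The sample code has the same terms plus treatment: "FCS REG(SBP4 = TRTPN AGE SEX RACE BMI ETHNIC SMK ALC BASE / DETAILS".

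Donors depend on the type of participant:
- Rule 2b, treatment-related stops: these "will be imputed using a control-based imputation from the sample of participants with intercurrent events and randomly assigned to placebo". Rule 3 treats non-adherent participants in the same way.
- Rule 4, adherent and event-free: "Participants without intercurrent events will have their missing result based on other participants also without intercurrent events and within the same treatment group".
- Two fallbacks follow. If samples are too small, "participants with and without intercurrent events will be included in the source sample for imputation". If the models do not converge, "model reduction (excluding covariates) may be performed".

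The primary model (SAP 3.10.2.2) is called an MMRM, but its code keeps only Week 4 rows, and its repeated structure is for site, not for visits within a participant.

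Home BP is also measured on one set day in the other weeks (Protocol 10.2.8) and sent automatically to the database (Protocol Appendix 3). SAP 3.10.2.1 averages it by week, for plots. Longitudinal models of all home SBP (SAP 3.10.3.1) and the tipping point analysis (SAP 3.10.2.7) are optional.

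**The concern.** A participant's own SBP in Weeks 2 and 3 should predict the missing Week 4 value better than smoking or alcohol does. Neither the imputation model nor the Week-4-only primary model uses it. Under rule 4, two people in the same arm with the same baseline and demographics get the same predicted value, even if one had responded well and the other had not.

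Rule 4 can include more than device failures. Missing pill returns are counted as pills taken, up to the logged days (SAP 3.9.1), so someone lost to follow-up may be classed as adherent. The Week 4 average is anchored to the clinic visit (SAP Table 3-2), so someone who misses FU1 has no defined window even if home readings continue.

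At stake is the accuracy of the effect size, if loss of the Week 4 value is related to on-treatment SBP and the relation differs between arms.

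**Working it through.** **Inputs from the documents.** SD 11 mmHg and difference 9 mmHg (Protocol 12.3, SAP 2.5); 100 vs 50 planned (SAP 2.5); 295 randomised (SAP 2.6.1) at 2:2:1; two-sided 5% (SAP 3.3).

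**Assumed, because the documents give no figure.** Rule 4 missing share m of 1-5% per arm; correlation of weekly with Week 4 SBP 0.7 (range 0.5-0.85); correlation of baseline with each of them 0.4; log-odds of missingness rising or falling by 1 per SD of weekly SBP.

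**1. The plan's own figure.** SE = 11 × √(1/100 + 1/50) = 1.905. Then 9/1.905 = 4.72, and Φ(4.72 − 1.96) = 99.7%, as SAP 2.5 states.

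**2. SE at the achieved size.** An exact 2:2:1 split of 295 is 118, 118 and 59. SE = 11 × √(1/118 + 1/59) = 1.75.

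**3. People involved.** At 1-2%, rule 4 covers 0.6-1.2 of 59 placebo participants and 1.2-2.4 of 118 in each GMRx2 arm.

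**4. Bias by hand.** When missingness is rare and the slope is 1, those missing average about 1 SD higher in weekly SBP. Their true Week 4 SBP is then 0.7 SD higher and their baseline 0.4 SD higher. A baseline-only model predicts 0.4 × 0.4 = 0.16 SD. The gap is (0.70 − 0.16) × 11 = 5.94 mmHg, and the bias in that arm is about m × 5.94. If the other arm loses people in the opposite direction, it doubles.

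| m | One arm selective: by hand / simulated | Opposite selection: by hand / simulated | Opposite, simulated, correlation 0.5-0.85 |
|---|---|---|---|
| 1% | 0.06 / 0.06 | 0.12 / 0.12 | 0.08-0.15 |
| 2% | 0.12 / 0.11 | 0.24 / 0.23 | 0.15-0.30 |
| 5% | 0.30 / 0.28 | 0.59 / 0.56 | 0.35-0.72 |

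Figures are in mmHg. The simulation used 2 million per arm, within-arm regression imputation and then ANCOVA on baseline. The sign depends on who is lost: losing GMRx2 non-responders inflates the effect, while losing GMRx2 good responders and placebo participants with high SBP shrinks it. With the same selection in both arms the bias in the difference is about 0.

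A second simulation, with a different set-up and only the active arm affected, gave 0.3-0.7 mmHg at a nominal 5%. It ran 500 trials per cell, so its Monte Carlo error is about 1.95/√500 = 0.09.

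**5. What adding weekly SBP recovers (5% missing, opposite selection).**
- Missingness depends on weekly SBP and all have readings: about 0 remains, by construction.
- Half of those missing also lack weekly readings: 0.28 of 0.56 remains.
- Missingness depends on Week 4 SBP itself: 0.52 of 0.88 remains.

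**6. Precision and power (planned size).** Arm variance is SD²/(n(1−m)) without weekly SBP and SD²[(1−R²)/(n(1−m)) + R²/n] with it, where R² is the share of residual Week 4 variance explained (assumed 0.25-0.65). At m = 2% the SE goes from 1.925 to 1.912-1.920, and at 5% from 1.955 to 1.923-1.942. Power at 9 mmHg goes from 99.67% to 99.68-99.70% at 2%, and from 99.59% to 99.62-99.67% at 5%.

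**7. Inference.** With d = bias/1.75, coverage is Φ(1.96 − d) − Φ(−1.96 − d): 94.8% at 0.23 mmHg and 93.8% at 0.56. Even at 0.56 toward the null, z = (9 − 0.56)/1.75 = 4.8.

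**The case against.** The strongest reply is that the plan already removes the obvious routes to BP-related loss. The listed events include "Discontinuation from the study treatment for reasons related to the study protocol or study treatment", covering lack of efficacy, tolerability and adverse events, and non-adherence goes to placebo donors. What is left under rule 4 is mostly device, transfer or scheduling trouble, where equal selection, and hence no bias, is at least as plausible as a slope of 1 in opposite directions.

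Missingness should also be low, since "calculations of averages will be performed if there is at least 1 valid BP measurement". Readings are telemonitored for schedule adherence (Protocol 10.2.8), diaries back up failed transfers (Appendix 3), FU1 has a window of ±7 days (Table 5), and those who stop treatment should still attend (Protocol 8.8). The Clinic BP Substitution analysis is committed (SAP 3.10.2.2), although it drops anyone without a clinic value at the visit, including anyone who missed FU1.

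This stands, and it is why the point is minor. It does not remove the gap for the few people in rule 4.

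A reader might infer more in three ways that the documents do not support:
- **That the gap reaches participants who stopped or did not adhere.** Rules 2b and 3 deliberately use placebo donors; on-treatment SBP would work against that intent.
- **That the small-sample fallback will merge donors and widen the problem.** Merging is possible but not established. Placebo adverse-event withdrawal rates of 1.6-5.2% in Protocol Table 2 give 0.9-3.1 of 59, but stops for lack of efficacy also count as events, and covariates may be dropped.
- **That add-on treatment makes this serious.** Add-on is not a listed intercurrent event, so these participants can fall under rule 4. Protocol 8.6 prompts review at home SBP above 160 on two consecutive measurement days, or above 170 on one. On assumed placebo means of 140 and 145, that is about 1.7-2.4% and 5.6-6.6% of placebo, before investigator judgement. Even at higher assumed rates (3.4-8.7%), with 10-50% of them missing Week 4 and an 8.5 mmHg add-on effect (midpoint of the 8-9 in Protocol 5.7), the current model is off by only 0.01-0.11 mmHg, toward the null. Unrestricted pre-add-on readings would be off by 0.02-0.22 away from it.

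**Conclusion.** The point holds as a minor, low-cost improvement. The planned imputation is valid under missing at random given its listed covariates; adding on-treatment SBP makes that assumption easier to defend for rule 4 participants.

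At an assumed 1-2% event-free missingness that depends on on-treatment SBP differently by arm, the bias is about 0.1-0.2 mmHg, and about 0.3-0.6 at 5%, in either direction. It is about zero if the dependence is equal. These sizes rest on the assumed missing rate, correlations and slope, none of which the documents give.

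A reader might infer that the primary result is unreliable or the trial underpowered. The figures do not support that: the SE is about 1.75, z stays near 4.8 in the 5% case with bias toward the null, and power changes by less than 0.1 percentage point at 2-5% missing.

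**What to change.** In SAP 3.10.2.6, for rule 4 only:

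1. Add one auxiliary predictor of Week 4 SBP: mean weekly home SBP from Day 8 to the day before the Week 4 averaging window opens (FU1 minus 7 days; nominal Day 21 if FU1 was missed). With FU1 on Day 28 this is Days 8-20. One summary term is safer than several, because the placebo group is small.
2. If the model must be reduced, drop smoking, alcohol and ethnicity before any BP term.
3. Leave rules 2 and 3 unchanged, and do not use the predictor if donors with and without events are merged.
4. For participants given add-on BP treatment, do not use readings taken before add-on; impute them with the current covariates.
5. If the data are already unblinded, run this as a labelled sensitivity analysis.

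The cost is SAP wording and a few lines of imputation code, with no new data. The downside is one more predictor that has gaps: weekly sets are only the ideal in Protocol Appendix 3, and device failure or disengagement can remove both weekly and Week 4 readings. Recovery may therefore be partial.
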